1.1. Changes to the Protocol Defined Statistical Analysis Plan

Due to the early termination of the study, the SAP has been developed for the purposes of an abbreviated CSR for reporting of primary and secondary endpoints and for the final safety update.

Intent-to-Treat Analysis Set changed to a Modified Intent-to-Treat. Participants who were first dosed or randomized after the date of dear investigator letter (DIL) requesting immediate discontinuation of GSK3359609/placebo will be excluded. The date of the DIL is the 13th April.

For the abbreviated CSR, exploratory, supplementary, sensitivity, subgroup analyses will not be performed. Minimally required safety analyses will be performed. For safety analyses, the between-treatment difference will not be analyzed.

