9.4.2. Safety Analyses

The safety population will serve as the primary population for the analyses of safety data in this study. Safety analyses will follow a tiered approach [Crowe, 2009] as shown in [Table 12](#). The tiers differ with respect to the analyses that will be performed. Tier 1 safety endpoints that will be critical to inferential testing for statistical significance with p-values and 95% confidence intervals may be provided for between-group comparisons.

For this protocol, there are no Tier 1 events. All safety parameters will be considered Tier 2 or Tier 3. Tier 2 parameters will be assessed via point estimates with 95% CI provided for between-group comparisons; only point estimates by treatment group are provided for Tier 3 safety parameters. The between-treatment difference will be analyzed using the Miettinen and Nurminen method.

Based on emerging external data, the analysis strategy for safety endpoints may be modified to improve the integrity and efficiency of the design. Should this happen, the change will be documented elsewhere, if not in a protocol amendment, at the earliest time before any unblinding of the data. Refer to the statistical analysis plan for further details.

Table 12 Analysis Strategy for Safety Parameters

Safety Tier	Safety Endpoint	95% CI for Treatment Comparison	Descriptive Statistics
Tier 2	Any AE	X	X
	Any Serious AE	X	X
	Any Grade 3-5 AE	X	X
	Any Treatment-Related AE	X	X
	Any Treatment-Related Serious AE	X	X
	Any Grade 3-5 and Treatment-Related AE	X	X
	Dose Modification due to AE	X	X
	Discontinuation due to AE	X	X
	Death	X	X
Tier 3	Specific AEs, SOCs (incidence \geq 5% of participants in 1 of the treatment groups)	X	X
	Specific AEs, SOCs (incidence $<$ 5% of participants in both treatment groups)		X
	Change from Baseline Results (Labs, ECGs, Vital Signs)		X

Abbreviations: AE=adverse event; CI=confidence intervals; ECG=electrocardiogram; SOC=system organ class

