1.2. Objectives, Endpoints and Estimands

1.2.1. Objectives and Endpoints

Objectives	Endpoints
Primary Objectives	Primary Endpoints

 Compare the efficacy of GSK3359609 in combination with pembrolizumab + 5FU-platinum chemotherapy versus placebo in combination with pembrolizumab + 5FU-platinum chemotherapy in the total population (PD-L1 CPS all) and in the PD-L1 positive (CPS\geq1) population 	
 OS in the total and the PD-L1 CPS\geq1 populations defined as the time from the date of randomization until the date of death due to any cause PFS per RECIST v1.1 by Investigator assessment in the total population; defined as the time from the date of randomization to the date of first documented disease progression or death due to any cause, whichever comes first
Secondary Objectives	Secondary Endpoints

 Further compare the efficacy of GSK3359609 in combination with pembrolizumab + 5FU-platinum chemotherapy versus placebo in 	
 PFS per RECIST v1.1 by Investigator assessment in the PD-L1 CPS\geq1 population

Objectives	Endpoints

 combination with pembrolizumab + 5FU-platinum chemotherapy 	
 Milestone OS rate at 12, 24 and 36 months in the total and the PD-L1 CPS ≥ 1 populations ORR per RECIST v1.1 by Investigator assessment in the total and the PD-L1 CPS ≥ 1 populations DCR per RECIST v1.1 by Investigator assessment in the total and the PD-L1 CPS ≥ 1 populations DoR per RECIST v1.1 by Investigator assessment in the total and PD-L1 CPS ≥ 1 populations

 Evaluate the safety and tolerability of GSK3359609 in combination with pembrolizumab + 5FU-platinum chemotherapy compared with placebo in combination with pembrolizumab + 5FU-platinum chemotherapy 	
 Frequency and severity of AEs, AESI, SAEs Dose modifications (i.e., interruptions, discontinuations)

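### SAP 1.1 drops the between-arm 95% CIs that protocol Table 12 plans for Tier 2 safety items, leaving a comparative safety objective with descriptive incidence only, apart from the OS hazard ratio

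*SAP*

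**What the plan says.** Protocol 9.4.2 sets a tiered safety analysis. It states that "Tier 2 parameters will be assessed via point estimates with 95% CI provided for between-group comparisons", and names the method: "The between-treatment difference will be analyzed using the Miettinen and Nurminen method". Table 12 has a column headed "95% CI for Treatment Comparison", marked for nine Tier 2 rows: any AE; serious AE; Grade 3-5 AE; treatment-related AE; treatment-related serious AE; Grade 3-5 treatment-related AE; dose modification due to AE; discontinuation due to AE; and death. No hypothesis test is attached: "For this protocol, there are no Tier 1 events".

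SAP 1.2.1 keeps the secondary objective: "Evaluate the safety and tolerability of GSK3359609 in combination with pembrolizumab + 5FU-platinum chemotherapy compared with placebo in combination with pembrolizumab + 5FU-platinum chemotherapy". SAP Section 1 says that the main CSR covers all primary and secondary endpoints.

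SAP 1.1, listing changes from the protocol after early termination, then says: "For safety analyses, the between-treatment difference will not be analyzed". What remains for safety (SAP 4.3.2 and 4.5) is counts and percentages of AEs, SAEs, AESIs, fatal events, discontinuations and deaths, with summaries of dose modifications.

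**The concern.** The objective asks for a comparison, the protocol specifies how to make it, and the SAP withdraws the comparison while leaving the objective as worded. The cut is also selective. SAP 4.3.2 keeps Miettinen-Nurminen differences with 95% CIs for ORR and DCR, and SAP 4.2.2 and 4.3.1.2 keep hazard ratios with 95% CIs for OS, PFS and time to deterioration. SAP 2.2 justifies one-sided testing partly by the drug's toxicity profile so far, and relies on two-sided intervals to reveal any detriment. No such interval is left for any adverse-event endpoint.

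At stake is how two columns of percentages will be read. Without an interval, a chance imbalance can be taken for harm, and a small observed difference can be taken as reassurance that the data are too few to give.

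**Working it through.** **Is the protocol text a pre-termination leftover?** The stop letter is dated 13 April 2021 and Amendment 2 is dated 30 June 2021. Amendment 2 revised Section 9.4 for reporting of the terminated study and left 9.4.2 and Table 12 standing. The SAP says that it is based on Amendment 2. So the two current documents differ on this analysis.

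**Does the protocol's modification clause cover the change?** The clause says that "the analysis strategy for safety endpoints may be modified to improve the integrity and efficiency of the design". Its stated trigger is emerging external data, and the change must be documented before any unblinding. SAP 1.1 gives early termination as its reason, and the text supplied does not place SAP version 3 relative to unblinding. The documents do not establish that the clause applies.

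**How wide would the restored intervals be?** The plan states no figure to reproduce. Inputs:
- Allocation 1:1 (protocol synopsis).
- Arm size: not given, so assumed at 25 to 150. The upper value is half of the roughly 300 participants planned for the Phase II/III stage (protocol 9.2).
- Event rate: 41%, the proportion with a serious event on GSK3359609 plus pembrolizumab without chemotherapy (protocol 2.3.1). It is illustrative; 70% is a second assumed value.

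The Miettinen-Nurminen limits are the values of δ at which

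z(δ) = (p̂₁ − p̂₂ − δ) / √{[p̃₁(1−p̃₁)/n₁ + p̃₂(1−p̃₂)/n₂] · N/(N−1)} = ±1.96,

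where p̃₁ and p̃₂ are the maximum-likelihood estimates under p̃₁ − p̃₂ = δ. Power for a true 15-point excess (56% v 41%, two-sided 5%) is

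Φ{[0.15 − 1.96√(2p̄(1−p̄)/n)] / √[(0.56×0.44 + 0.41×0.59)/n]}, with p̄ = 0.485.

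Half-widths are in percentage points for equal observed rates, with counts rounded to whole participants.

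| Per arm | 41% | 70% | Power, 15-point excess |
|---|---|---|---|
| 25 | 26.6 | 24.9 | 18% |
| 50 | 19.0 | 17.9 | 32% |
| 75 | 15.6 | 14.7 | 45% |
| 100 | 13.6 | 12.7 | 57% |
| 150 | 11.1 | 10.4 | 74% |

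Hand check at 150 per arm: 1.96 × √(2 × 0.41 × 0.59/150) = 0.111.

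As an example, 56/100 against 41/100 gives a difference of 15 points with 95% CI 1.1 to 28.3. With 28/50 against 20/50 the difference is 16 points with CI −3.7 to 34.5. The two pairs of percentages look almost the same, but only the first interval excludes zero.

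**What does the retained mortality contrast give?** With SE(log HR) ≈ 2/√d at 1:1, an observed HR of 1.0 has a 95% CI of 0.54-1.86 with d = 40 deaths, 0.68-1.48 with 100, and 0.71-1.40 with 136. The death counts are assumed; 136 is the planned first interim count in the paused design. This interval says nothing about Grade 3-5, serious or treatment-related events.

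**Which participants would be compared?** In SAP Section 3 the mITT set excludes anyone randomized or first dosed after the letter. The Safety set has no such cut-off, and it assigns participants to GSK3359609 only if they received a dose of it. Someone randomized to GSK3359609 but given only the backbone would therefore fall outside that group.

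**The case against.** The best defence is that this is an open scope cut. It sits in the section that lists departures from the protocol, and the version history explains that only minimally required safety output is kept for an abbreviated report. That stands: nothing is concealed.

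It can also be said that protocol 9.1.2 has the remaining secondary endpoints summarized descriptively, and that there are no Tier 1 events. This rules out hypothesis tests, but not intervals: ORR and DCR fall under the same sentence and still receive between-arm CIs.

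A third argument is that readers can compute the intervals. From per-arm counts they can, in unstratified form. The AE text does not say outright that tables are by arm, although the Safety set grouping implies it. An analysis planned for a secondary objective should still not be left to the reader.

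Finally, the intervals would be wide and often inconclusive. This is true, and it is what the reader needs to see.

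A reader might go further and infer that the CSR cannot say whether the stopped drug added harm. The documents do not support that: incidence of AEs, SAEs and deaths remains, the counts can be contrasted or pooled, and the OS hazard ratio with its two-sided 95% CI can show excess mortality. Nor do they say that GSK3359609 was stopped for toxicity; the SAP version history links the decision to an interim analysis.

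**Conclusion.** The concern holds in a limited form. The SAP removes the Tier 2 between-arm intervals that the current protocol plans, without restating the comparative objective and for a reason other than the one the protocol's modification clause names. The loss is the formal estimate and the display of its imprecision, about ±11 to ±27 points for a 41% event rate. It is not a loss of the underlying data, and mortality remains contrasted. The widths rest on assumed arm sizes and an illustrative event rate. This is a cheap improvement that helps the trial answer its own objective; it does not block the analysis.

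**What to change.** Replace the sentence in SAP 1.1 so that the main CSR includes one table of unstratified Miettinen-Nurminen risk differences with 95% CIs, and no p-values, for the nine Tier 2 rows of protocol Table 12. Restrict it to participants randomized and first dosed on or before the 13 April letter. State that grouping follows treatment received, so the contrast is close to the randomized one but not identical to it.

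Do not repeat the table on post-discontinuation data in the final safety update. Participants could stay on pembrolizumab and chemotherapy after GSK3359609/placebo stopped, and later events would dilute any difference. If it is repeated, limit events to the GSK3359609/placebo exposure period plus the windows in protocol 8.3.1 (30 days for AEs, 90 days for SAEs and AESIs).

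The cost is one extra table with wide intervals. The SAP already uses the stratified form of the method for ORR and DCR in the mITT set, so the unstratified version needs only a small programming change.

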1.2. Objectives, Endpoints and Estimands

1.2.1. Objectives and Endpoints

Objectives	Endpoints
Primary Objectives	Primary Endpoints

 Compare the efficacy of GSK3359609 in combination with pembrolizumab + 5FU-platinum chemotherapy versus placebo in combination with pembrolizumab + 5FU-platinum chemotherapy in the total population (PD-L1 CPS all) and in the PD-L1 positive (CPS\geq1) population 	
 OS in the total and the PD-L1 CPS\geq1 populations defined as the time from the date of randomization until the date of death due to any cause PFS per RECIST v1.1 by Investigator assessment in the total population; defined as the time from the date of randomization to the date of first documented disease progression or death due to any cause, whichever comes first
Secondary Objectives	Secondary Endpoints

 Further compare the efficacy of GSK3359609 in combination with pembrolizumab + 5FU-platinum chemotherapy versus placebo in 	
 PFS per RECIST v1.1 by Investigator assessment in the PD-L1 CPS\geq1 population

Objectives	Endpoints

 combination with pembrolizumab + 5FU-platinum chemotherapy 	
 Milestone OS rate at 12, 24 and 36 months in the total and the PD-L1 CPS ≥ 1 populations ORR per RECIST v1.1 by Investigator assessment in the total and the PD-L1 CPS ≥ 1 populations DCR per RECIST v1.1 by Investigator assessment in the total and the PD-L1 CPS ≥ 1 populations DoR per RECIST v1.1 by Investigator assessment in the total and PD-L1 CPS ≥ 1 populations

 Evaluate the safety and tolerability of GSK3359609 in combination with pembrolizumab + 5FU-platinum chemotherapy compared with placebo in combination with pembrolizumab + 5FU-platinum chemotherapy 	
 Frequency and severity of AEs, AESI, SAEs Dose modifications (i.e., interruptions, discontinuations)

 Compare disease and treatment related symptoms and impact on function and HRQoL of GSK3359609 in combination with pembrolizumab + 5FU-platinum chemotherapy versus placebo in combination with pembrolizumab + 5FU-platinum chemotherapy 	
 The time to deterioration in Pain measured by the EORTC QLQ-H&N35 pain domain in the total and PD-L1 CPS ≥ 1 populations The time to deterioration in Physical Function measured by the PROMIS-PF-8c in the total and PD-L1 CPS ≥ 1 populations
Exploratory Objectives	Exploratory Endpoints

 Compare the efficacy of GSK3359609 in combination with pembrolizumab + 5FU-platinum chemotherapy to placebo in combination with pembrolizumab + 5FU-platinum chemotherapy 	
 ORR, DCR, DoR (sample-size permitting), PFS per iRECIST in the total population PFS2, defined as the time from the date of randomization to the date of second objective disease progression per RECIST v1.1, or death due to any cause, whichever first in the total population

 Evaluate and compare disease and treatment related symptoms and impact on function and HRQoL of GSK3359609 in combination with pembrolizumab and 5FU-platinum chemotherapy versus placebo in combination with 	
 Symptomatic AEs as measured by the FACT GP5 Changes in other domains of quality of life as measured by the selected EORTC IL50/51 (subset of domains of the

Objectives	Endpoints
pembrolizumab and 5FU-platinum chemotherapy	EORTC QLQ-C30 and EORTC QLQ-H&N35), BPI-I3 and EQ-5D-3L

 Evaluate healthcare resource utilization of participants in the GSK3359609 combination with pembrolizumab arm versus participants in the placebo combination with pembrolizumab arm 	
 Non-protocol healthcare encounters, such as provider visits, emergency room visits, hospitalizations, medications, tests, or procedures

 Evaluate GSK3359609 PK properties 	
 Summary of GSK3359609 concentrations and Cmax, Ctrough

 Determine immunogenicity of GSK3359609 	
 Anti-drug antibody (ADA) incidence

 Explore relationship between biomarkers in tumour and blood, such as immune response biomarkers, target expression and efficacy endpoints 	
 Tumor and blood-based analysis of DNA, RNA, and protein analytes/profiles; OS, PFS, ORR, other efficacy parameters

 Genetics Research: Investigate the relationship between host genetic variations and response to therapy 	
 Germline genetic evaluations may be conducted for: 
 Clinical response, including GSK3359609/ pembrolizumab or any concomitant medicines Disease susceptibility, severity, and progression and related conditions

Abbreviations: AE=adverse events; AESI=adverse events of special interest; Brief Pain Inventory-Item 3=BPI-I3; DCR=disease control rate; DNA=deoxyribonucleic acid; DoR=duration of response; EORTC QLQ-C30=European Organisation for Research and Treatment of Cancer Quality of Life Questionnaire 30-item Core Module; EORTC H&N35=EORTC Head and Neck 35 Item Module; EQ-5D-3L=EuroQoL 5 Dimensions; FACT-GP5 = Functional Assessment of Cancer Therapy – General (Item GP5); HRQoL= health-related quality of life; iPFS = immune-based progression-free survival; iRECIST=immune-based Response Evaluation Criteria in Solid Tumors; ORR=overall response rate; OS=overall survival; PFS=progression-free survival; PROMIS-PF-8c= Patient-Reported Outcomes Measurement Information System-Physical Function-Short Form; RECIST= Response Evaluation Criteria in Solid Tumors; RNA=ribonucleic acid

1.2.2. Estimands

Primary and key secondary study objectives are presented in [Table 2](#) with additional information, including prespecified estimands with related attributes.

Due to early study termination, only the primary estimands will be reported in the main CSR.

Table 2 Estimands

Objective (Hypothesis ¹)	Estimand Category	Estimand			
		Variable/ Endpoint ²	Population of interest (Analysis Set)	Intercurrent Event Strategy ³	Population Level Summary Measure

Primary Objective 1:
 
To demonstrate the superiority of GSK3359609 in combination with pembrolizumab + 5FU-platinum chemotherapy compared to pembrolizumab+ 5FU-platinum therapy in OS in the total and PD-L1 CPS ≥ 1 populations in R/M HNSCC (H1, H2)
	Primary	OS	
 Total population (mITT) PD-L1 CPS ≥ 1 population (mITT) 	
 New anti-cancer therapy: treatment policy Treatment discontinuation: treatment policy 	Hazard ratio for GSK3359609+pembrolizumab + 5FU-platinum chemotherapy vs. placebo+pembrolizumab + 5FU-platinum chemotherapy

Primary Objective 2:
 
To demonstrate the superiority of GSK3359609 in combination with pembrolizumab + 5FU-platinum chemotherapy compared to placebo in combination with pembrolizumab + 5FU-platinum chemotherapy in PFS in total population R/M HNSCC (H3)
	Primary	PFS	
 Total population (mITT) 	
 New anti-cancer therapy: hypothetical Treatment discontinuation: treatment policy ≥ 2 missed disease assessments: hypothetical Death: composite 	Hazard ratio for GSK3359609+pembrolizumab + 5FU-platinum chemotherapy vs. placebo+pembrolizumab + 5FU-platinum chemotherapy

[figure not shown]
Objective (Hypothesis ¹)	Estimand Category	Estimand			
		Variable/ Endpoint ²	Population of interest (Analysis Set)	Intercurrent Event Strategy ³	Population Level Summary Measure

Key Secondary Objective 1:
 
To demonstrate the superiority of GSK3359609 in combination with pembrolizumab + 5FU-platinum chemotherapy compared to placebo in combination with pembrolizumab + 5FU-platinum chemotherapy in PFS in PD-L1 CPS \geq1 R/M HNSCC
 
(H4)
	Primary	PFS	
 • PD-L1 CPS \geq1 population (mITT) 	
 • New anti-cancer therapy: hypothetical • Treatment discontinuation: treatment policy • \geq2 missed disease assessments: hypothetical • Death: composite 	Hazard ratio for GSK3359609+pembrolizumab + 5FU-platinum chemotherapy vs. placebo+pembrolizumab + 5FU-platinum chemotherapy

Key Secondary Objective 2:
 
To demonstrate the superiority of GSK3359609 in combination with pembrolizumab + 5FU-platinum chemotherapy compared to placebo in combination with pembrolizumab + 5FU-platinum chemotherapy in TTD in pain in total population and PD-L1 CPS \geq1 R/M HNSCC
 
(H5, H6)
	Primary	TTD in pain	
 • Total population (mITT) • PD-L1 CPS \geq1 population (mITT) 	
 • New anti-cancer therapy: hypothetical • Treatment discontinuation: treatment policy • Disease progression per RECIST v1.1 or iRECIST: treatment policy • Death: treatment policy • \geq2 missed corresponding PRO assessments if at least 	Hazard ratio for GSK3359609+pembrolizumab + 5FU-platinum chemotherapy vs. placebo+pembrolizumab + 5FU-platinum chemotherapy

Objective (Hypothesis ¹)	Estimand Category	Estimand			
		Variable/ Endpoint ²	Population of interest (Analysis Set)	Intercurrent Event Strategy ³	Population Level Summary Measure
				one missed assessment is due to the participant being too ill: hypothetical	

Key Secondary Objective 3:
 
To demonstrate the superiority of GSK3359609 in combination with pembrolizumab + 5FU-platinum chemotherapy compared to placebo in combination with pembrolizumab plus placebo + 5FU-platinum chemotherapy in TTD in PF in total population and PD-L1 CPS \geq1 R/M HNSCC
 
(H7, H8)
	Primary	TTD in PF	
 Total population (mITT) PD-L1 CPS \geq1 population (mITT) 	
 New anti-cancer therapy: hypothetical Treatment discontinuation: treatment policy Disease progression per RECIST v1.1 or iRECIST: treatment policy Death: treatment policy \geq2 missed corresponding PRO assessments if at least one missed assessment is due to the participant being too ill: hypothetical 	Hazard ratio for GSK3359609+pembrolizumab + 5FU-platinum chemotherapy vs. placebo+pembrolizumab + 5FU-platinum chemotherapy

Abbreviations: iRECIST=immune-based Response Evaluation Criteria in Solid Tumors; mITT =Modified Intent-to-Treat; OS = overall survival; PF = physical function; PFS = progression free survival; PRO = Patient Reported Outcomes; RECIST = Response Evaluation Criteria in Solid Tumors; TTD = time to deterioration.

1. Refer to Section 2 for details in the hypotheses.
2. Refer to Section 4 for the definition of variable/endpoint.
3. Refer to Section 4.2.1 and Section 5.3 for details in the two or more missed disease assessments.

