Since PFS is interval censored, extended loss to follow-up prior to PD or death increases the uncertainty when the event occurs. As such, PFS will be analyzed censoring for extended time without an adequate assessment to account for missed response assessments prior to disease progression or death. Specifically, if there are two or more assessments which are missing followed by an assessment of PD or death, PFS will be censored at the last adequate assessment prior to PD or death.

A summary of the assignments for progression and censoring dates for the primary analysis of PFS per RECIST v1.1 is also illustrated in [Table 3](#).

Table 3 Censoring Rules for Primary Analysis of PFS per RECIST v1.1

Situation	Primary Analysis
No or incomplete baseline disease assessments and the participant has not died	Censored at the date of randomization
No adequate ¹ post-baseline disease assessments (prior to anticancer therapy, if initiated) and the participant has not died ²	Censored at the date of randomization
With adequate post-baseline disease assessments, new anticancer treatment is not initiated, and no documented PD or death	Censored at the date of last adequate radiological disease assessment
With adequate post-baseline disease assessments before the start of new anticancer therapy, and new anticancer treatment is initiated (prior to documented PD or death) ³	Censored at the date of last adequate radiological disease assessment on or prior to starting new anticancer treatment
PD or death documented after ≤ 1 missed disease assessment ⁴	Progressed at the date of documented PD ⁵ or death, whichever occurs first
PD or death documented after ≥ 2 missed disease assessments ^{4,6}	Censored at the date of last adequate radiological disease assessment prior to the ≥ 2 missed disease assessment ⁷

Abbreviations: CR=complete response; PD=progressive disease; PFS=progression-free survival; PR=partial response; RECIST=response evaluation criteria in solid tumors; SD=stable disease

1. An adequate assessment is defined as an assessment where the investigator assessed response is CR, PR, or SD
2. In case participant has documented PD but no other adequate assessments, see scenarios below.
3. If PD and new anti-cancer therapy occur on the same day, it is assumed that the progression was documented first (i.e., outcome is progression; the date is the date of the assessment for progression).

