4.3. Secondary Endpoint(s) Analysis

4.3.1. Key/Confirmatory Secondary Endpoint(s)

4.3.1.1. Definition of Endpoint

Time to Deterioration (TTD) in Pain and Physical Function (PF)

Time to deterioration (TTD) is defined as the time from randomization to the first definitive meaningful deterioration from baseline in the EORTC IL51 pain domain score and the TTD in Physical Function (PF) score. Deterioration is defined as an increase in the EORTC IL51 pain domain and a decrease in physical function as measured by the PROMIS-PF-8c. Specifically, the deterioration has to be:

- Meaningful, i.e. greater than a clinically meaningful within-individual change in score, as defined below;
- Definitive, i.e. all subsequent assessment of the score are also showing a clinically meaningful deterioration compared with baseline, or no further score is available for the participants for any reason (including discontinuation, disease progression or death).

Participants who don't show meaningful deterioration will be censored at the time of the last available PRO assessment within the pain domain of EORTC IL51 for TTD in pain or within PROMIS-PF-8c for TTD in PF. For TTD in pain or TTD in PF, the determination of dates of deterioration events and dates for censoring are summarized in [Table 4](#).

Table 4 Censoring Rules for Analysis of TTD

Situation	Primary Analysis
No or incomplete baseline corresponding PRO assessments	Censored at the date of randomization
No post-baseline corresponding PRO assessments	Censored at the date of randomization
With post-baseline corresponding PRO assessments, new anticancer treatment is not initiated, and no deterioration	Censored at the date of last available corresponding PRO assessment
With post-baseline corresponding PRO assessments, and new anticancer treatment is initiated (prior to deterioration) ¹	Censored at the date of last available corresponding PRO assessment on or prior to starting new anticancer treatment
Deterioration after ≤ 1 missed corresponding PRO assessment ²	Deteriorated at the date of deterioration
Deterioration after ≥ 2 missed corresponding PRO assessments if at least one missed assessment is due to the participant being too ill ^{2,3}	Censored at the date of last available corresponding PRO assessment prior to the ≥ 2 missed corresponding PRO assessment

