4.3.1.2. Main analytical approach

PFS per RECIST v1.1 in PD-L1 CPS ≥ 1

PFS per RECIST v1.1 in PD-L1 CPS ≥ 1 participants will be analyzed and reported similarly to the primary analysis of PFS in PD-L1 CPS all participants as described in Section 4.2.2.

Time to Deterioration (TTD) in Pain and Physical Function (PF)

The time to deterioration (TTD) in Pain measured by the EORTC IL51 pain domain and the TTD in Physical Function (PF) measured by the PROMIS-PF-8c will be analyzed separately for the PD-L1 total and CPS ≥ 1 group using the non-parametric Kaplan-Meier method. Kaplan-Meier plots of TTD will be presented by study intervention. Kaplan-Meier estimates for the median TTD and the first and third quartiles will be presented, along with 95% CIs. CIs for quartiles will be estimated using the Brookmeyer-Crowley method (1982). The TTD for both treatment groups will be compared by the stratified log-rank test.

A stratified Cox proportional hazard model with Efron's method of tie handling will be used to assess the magnitude of the treatment difference (i.e., the hazard ratio). The hazard ratio and its 95% confidence interval from the stratified Cox model with a single treatment covariate will be reported separately for the PD-L1 total and CPS ≥ 1 group. Participants with no post-baseline assessments will be considered censored at day 1 and participants without definitive meaningful clinical deterioration for the PRO score will be treated as censored for that PRO score at the last visit.

Only if GSK3359609 in combination with pembrolizumab + 5FU/platinum-based chemotherapy demonstrates superiority to placebo in combination with pembrolizumab + 5FU/platinum-based chemotherapy in OS in both populations (total and PD-L1 CPS ≥ 1 participants), will key secondary PRO endpoints be tested. The alpha level from OS hypothesis will be propagated to key PRO hypotheses as described in Section 2.2.

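### SAP Table 2 labels death as treatment policy for time to deterioration (H5-H8), but the written rules censor deaths that occur without a recorded deterioration

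*SAP*

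**What the plan says.** SAP 1.2.2, Table 2, lists "Death: treatment policy" among the intercurrent-event strategies for TTD in pain (H5, H6) and again for TTD in physical function (H7, H8). For PFS the same table has "Death: composite". The summary measure for all of them is the hazard ratio.

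SAP 4.3.1.1 defines the endpoint: "Time to deterioration (TTD) is defined as the time from randomization to the first definitive meaningful deterioration from baseline". Death is not an event in itself. Participants without meaningful deterioration, for the pain endpoint, "will be censored at the time of the last available PRO assessment within the pain domain of EORTC IL51"; physical function has the parallel rule. SAP 4.3.1.2 repeats the idea: "participants without definitive meaningful clinical deterioration for the PRO score will be treated as censored for that PRO score at the last visit". Protocol 9.4.3 also censors at the last available PRO assessment.

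Table 4 of the SAP has no row for death. Death is named once in the TTD definition: a deterioration counts as definitive if no later score exists for any reason, death included.

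SAP 4.3.1.2 plans Kaplan-Meier plots, medians and quartiles, a stratified log-rank test and a stratified Cox model.

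**The concern.** Treatment policy means using the outcome whatever happens after the intercurrent event. After death there is no outcome to use, so the label describes something that cannot be done. The censoring rules do something else. A reader of the estimand table would think that deaths had been accounted for, when most deaths without deterioration simply leave the risk set.

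This affects how the TTD results can be read. Under the protocol's control-arm survival, 23% have died by 6 months and 47% by 12, so death is a large competing event. The mislabelled strategy also reaches the report: SAP 1.2.2 says that the primary estimands are the ones in the main CSR, and SAP 4.2.3 and 4.2.4 drop sensitivity and supplementary analyses. No other planned TTD analysis would show what the deaths do.

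**Working it through.** **Which rule catches a death**

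| Course before death | Rule in SAP 4.3.1.1 | Result |
|---|---|---|
| Last score deteriorated, then death | no-further-score clause | event at the deterioration date |
| Scores without deterioration, no new therapy, then death | "With post-baseline corresponding PRO assessments, new anticancer treatment is not initiated, and no deterioration" | censored at last PRO |
| No score after baseline, then death | "No post-baseline corresponding PRO assessments" | censored at randomization |

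The last row carries no condition that the participant is alive. The PFS rules do: "No or incomplete baseline disease assessments and the participant has not died". So the SAP draws this distinction for PFS and not for TTD, and the TTD censoring of deaths arises by default.

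**Death rate from the plan**

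Protocol 9.2.1 gives control survival of 77%, 53.0% and 29.4% at 6, 12 and 24 months, with a median of 13 months. Piecewise-constant hazards per month:
- 0-6 months: -ln(0.77)/6 = 0.0436
- 6-12 months: ln(0.77/0.53)/6 = 0.0623
- 12-24 months: ln(0.53/0.294)/12 = 0.0491

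The implied median is 12 + ln(0.53/0.50)/0.0491 = 13.2 months, which reproduces the stated 13.

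**Kaplan-Meier against cumulative incidence**

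The documents give no deterioration rate, so the hazard a is assumed at 0.06 to 0.10 per month, independent of death, with no other censoring. With death hazard b:
- One minus Kaplan-Meier, deaths censored: 1 - exp(-a t)
- Cumulative incidence with death competing: a/(a+b) × [1 - exp(-(a+b) t)]

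For a = 0.08 and b = 0.0436:
- 6 months: 1 - exp(-0.48) = 38.1%, against 0.6475 × (1 - 0.4765) = 33.9%
- 12 months: 1 - exp(-0.96) = 61.7%, against 0.6475 × (1 - 0.2270) = 50.0%

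Holding b at its 0-6 month value implies 0.77² = 59% survival at 12 months, not the stated 53%. Using 0.0623 for months 6-12, the 12-month cumulative incidence is 33.9% + 0.4765 × 0.5624 × 0.5741 = 49.3%.

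| a per month | Gap at 6 months | Gap at 12, constant b | Gap at 12, piecewise b |
|---|---|---|---|
| 0.06 | 3.4 points | 10.1 | 10.8 |
| 0.08 | 4.2 | 11.7 | 12.4 |
| 0.10 | 4.9 | 12.7 | 13.5 |

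Over a wider range of assumed TTD medians, 6 to 24 months, the piecewise gap at 12 months is 7 to 14 points.

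**Unequal deaths by arm**

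Give both arms the same deterioration hazard (assumed median 12 months) and let deaths differ by the target OS hazard ratio of 0.72. The Kaplan-Meier curves coincide. The 24-month cumulative incidence is 49.8% in control and 55.2% in the experimental arm, because more of the latter live long enough to deteriorate.

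**Dependence**

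A simulation of 400,000 participants used the PRO schedule in SAP 5.3, an assumed TTD median of 12 months, permanent deterioration, and assumed Gaussian-copula correlations between deterioration and death.

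| Correlation | One minus KM at 12 months | Cumulative incidence | Value without death |
|---|---|---|---|
| 0 | 49.2% | 38.0% | 50% |
| 0.3 | 44.8% | 35.6% | 50% |
| 0.6 | 40.6% | 33.0% | 50% |

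Across these runs, 64% to 75% of deaths by 12 months had no recorded deterioration and were censored; 4% to 7% became events only through the no-further-score clause.

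**The case against.** The label has a defensible partial meaning: a deterioration counts regardless of a later death, which is what the no-further-score clause provides. That stands, and it rules out the inference that the analysis censors all deaths. It does not cover deaths without deterioration, which are most of the deaths in the simulation.

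A reader might infer that the Kaplan-Meier curve shows a population in which nobody dies. That needs independence of death and deterioration given strata, and the documents do not establish it. With positive dependence the curve falls short of that target too. A reader might also infer that Kaplan-Meier overstates deterioration outright. It does so only relative to cumulative incidence, which is a different quantity; relative to the no-death value it can understate.

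The estimand's summary measure is the hazard ratio. Neither it nor the log-rank test is altered by the label, so no planned test is wrong on this account.

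Practical weight is low. Amendment 2 removed PRO collection. At most about 15 months separate the original protocol (January 2020) from the letter stopping GSK3359609 or placebo (April 2021), so few participants can inform a 12-month estimate. TTD is tested only if OS succeeds in both populations. The CSR is deliberately abbreviated, and deaths and OS by arm are reported anyway. All of this stands, but those outputs do not show deaths without prior deterioration.

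The SAP version history moves PRO analysis details to a standalone plan. The label and Table 4 remain in this SAP, and no other document can make treatment policy workable after death.

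**Conclusion.** The stated strategy for death is wrong as written for H5-H8. The rules give a cause-specific hazard ratio among participants alive and under PRO follow-up. The Kaplan-Meier curves, medians and quartiles can be read as deterioration in the absence of death only under independence given strata.

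One minus Kaplan-Meier exceeds the proportion who actually deteriorate by about 3-5 points at 6 months and 10-13, or slightly more, at 12. Those sizes rest on assumed deterioration hazards of 0.06-0.10 per month, independence, and the protocol's control survival. The mismatch itself rests on none of these.

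Calling the whole strategy hypothetical would also go too far: that fits the Kaplan-Meier curve, while the hazard ratio is closer to while-alive. This is a minor correction to labelling and reporting.

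**What to change.** 1. In SAP Table 2, for H5-H8, replace the death entry with what the rule does: while-alive (cause-specific) for the hazard ratio, hypothetical for the Kaplan-Meier curve.
2. Add a death row to Table 4: death without prior definitive deterioration is censored at the last available PRO, or at randomization if there is none after baseline. State beside it that a deteriorated last score followed by death is an event.
3. Report the number of deaths without prior deterioration by arm, and show the cumulative incidence of deterioration, with death as a competing event, beside the Kaplan-Meier curve.

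The cost is two table edits, one count and one figure in the abbreviated CSR. No new data are needed.
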